 - d. Maintaining participant's research records: **Project Director**
 - e. Completing physical examination: N/A
 - f. Taking vital signs, height, weight: N/A
 - g. Drawing / collecting laboratory specimens: N/A
 - h. Performing / conducting tests, procedures, interventions, questionnaires: **PI & Project Director**
 - i. Completing study data forms: **Project Director**
 - j. Managing study database: **Project Director**

L. Assessment of Subject Safety and Development of a Data and Safety Monitoring Plan

1. **Responsible parties:** The **Principal Investigator (PI)** will be responsible for overall assurance and monitoring of safety of participants and integrity of data in conduct of both phases of the proposed study. This includes continuous active review of research activities that will be completed with assistance of the Project Director. The PI will be

responsible for submitting necessary reports (including minutes of annual and any additional SMC meetings) to the National Institute on Aging (NIA). The PI will provide timely reporting to NIA of a) any unanticipated problems or unexpected serious adverse events that are determined to be related to the study protocol, b) IRB-approved revisions to the study protocol that indicate a change in risk for participants, c) a summary of recommendations made by the SMC and if applicable the action plan for response, and) notice of any actions taken by the IRB or regulatory bodies regarding the research and any responses to those actions.

In addition, an expert **Safety Monitoring Committee (SMC)** will provide oversight to assure the safety of participants and integrity of the data. The members of the SMC include a team of interdisciplinary professionals who are not a part of the research team. Per direction of the NIA program officer responsible for this FOA, members of the committee will be identified upon funding of the study. It is anticipated that the SMC members include clinical and research experts on NH dementia care and NH staff education as well as a statistician.

2. **Data/events/frequency of review:** The **SMC** will initially review and approve the written study protocol, data collection and storage protocols, intervention materials, informed consent procedures, and this plan for data and safety monitoring. Any outside agreements with vendors and subcontractors will be reviewed. The SMC will also review the general reporting guidelines based on the study procedures approved by IRB. Reporting rules will be established taking into consideration the population under study and anticipated adverse outcomes (reflected in the human subjects consent documents). Prior to study implementation, the SMC will identify pre-specified stopping rules that will be employed if significant benefits or risks have developed, if trial management issues prevent successful completion, or if compelling ethical concerns arise. The PI and other research team members as delegated will conduct an audit at least annually including review of a random sample of at least 3 CNAs who participate in CHATO training and participate in audio recording for compliance with study protocols including informed consent documents, data storage documentation and deidentification of data. The SMC will meet annually and additionally if needed at the request of the PI (due to issues arising in study conduct or major changes in study protocols). The SMC will review reports of the research team concerning data quality and timeliness, adherence to study protocols, participant recruitment and accrual, and consenting procedures. The research team (under the direction of the PI) will report accrual, retention figures, and all adverse and other events and outcomes.
3. **Types of analyses to be performed:** At the end of the first year, the research team will generate summary analyses of results for primary outcomes. The annual SMC meeting will include evaluation of these interim data analyses to evaluate the need for revising or stopping the study.
4. **Safety-related triggers that would cause the PI to stop or alter the study:**
 - a. **Adverse occurrences** (untoward or unfavorable medical occurrences in a human subject, including any abnormal sign, symptom, or disease, temporally associated with the subject's participation in the research study, whether or not considered related to the subject's participation in the research) will be identified by all research team members and promptly reported to the PI (and recorded on an adverse occurrence report sheet). The PI will review all reports to determine whether the event is 1) unexpected, 2) is related or potentially related to the research study participation and 3) suggests that the research places subjects or others at a greater risk of harm related to the research than was previously known or recognized⁸⁸. If these three conditions exist, the occurrence will be considered an adverse event and will be immediately reported to the IRB on the appropriate form and to the SMC for review⁸⁹. The SMC will review all adverse occurrence reports (including those that do not meet criteria for adverse events) at annual meetings. Because the NH staff participants are participating in a

behavioral intervention and some staff will passively record care sessions, there is minimal risk of adverse events in this study. NH residents who staff interact with are not likely to be adversely affected by changes in staff communication after the CHATO training. Through these reviews of adverse events and occurrences, the SMC will consider whether cumulative data indicates the need to change the research design, to modify information presented to participants, or to terminate the project. It is anticipated that the committee may decide that due to minimal risk in this behavioral intervention study, there is not a risk for severe adverse events that would require a-priori stopping rules (this decision will be reviewed at least annually by the SMC)². Any action taken to suspend or terminate the project will be reported to the respective IRB, the NIH Office of Sponsored Projects, and the program director at NIA. New, scientific developments outside the study that may impact participant safety, or the ethics of the study are considered in making these determinations.

- b. **New Developments:** The PI and SMC will monitor media, professional presentations, and scientific literature for breaking scientific developments regarding new developments, safety, and ethics that could impact the study. These will be reviewed at each annual SMC meeting. The SMC will evaluate the final study manuscripts and final reports to assure results are fairly presented and conclusions are appropriate.

III. Subject Participation

A. Recruitment:

1. Recruitment will be conducted at the 7 nursing homes involved in the study. The feasibility nursing home is in Kansas City, KS and the 6 nursing homes in the clinical trial are on the Western Slope of Colorado. All the staff at the nursing homes will be invited to participate in the CHATO training and 12 CNAs at each nursing home will be recruited to evaluate the feedback app effects.
2. The PI and Project Director will work directly with the leadership and staff at the nursing homes to recruit voluntary participants. Presentations at staff meetings will be conducted to inform direct care staff at the nursing homes of the training, app, and research. An information sheet about the project will be provided to staff. The project director will meet with interested CNAs to further explain research, answer questions, and gain consent.

B. Screening Interview/questionnaire: CNAs who participate in audio recording will be at least 18 years old (have legal right to provide consent), speak fluent English, and be permanently employed in the NH. The Project Director will meet with interested CNAs and confirm they meet the eligibility criteria.

C. Informed consent process and timing of obtaining of consent

1. Only trained research team members who have completed the NIH-approved Human Subjects' protection certification will obtain informed consents. The research team will give subjects detailed and comprehensive information about the study and obtain their written consent. The consenting process will be a private conversation between the research team member and the interested CNAs in the nursing home. Written information will be provided to the CNAs and time will be allowed for thoughtful decision-making prior to consent. Consent includes the standard elements: a study description, the potential risks, benefits and options for non-participation. Permission will be obtained to use data (including audio recordings) for secondary data analysis, use in scholarly presentations, and for training caregivers. Signed consent for administrators and CNAs participating in recording will be obtained and kept in a locked file in the study office.
2. The consent process will be CNA-driven to avoid coercion and the voluntary nature of participation will be stated upfront. Due to the time commitment and extra effort of CNAs participating in the audio recordings, they will be paid a \$50 incentive to acknowledge their efforts and to encourage ongoing participation in each recording session. This small

financial token will be awarded after completing the recording sessions before and after CHATO completion to acknowledge participation and is not large enough to be construed as coercive ^{7,8}. Use of small financial incentive is reasonable to convey respect to research participants in exchange for their time and associated burden and has been found to enhance participation ⁹.

3. To guarantee confidentiality, a unique code number that has no connection to identification of subjects will be assigned to all staff and resident data. A list that links the assigned code number to the subjects' identifying information will be kept by the PI in a secure file and not disclosed to research assistants or others. Descriptive information for CNA participants recording participants will include age, gender, race and ethnicity, years of education, and experience working in long term care. No protected health information (PHI) will be collected from NH staff.

D. Alternatives to Participation: All staff at the nursing homes will have access to the CHATO training and participation in the audio recording is voluntary.

E. Costs to Subjects: N/A

F. How new information will be conveyed to the study subject and how it will be documented: Any new information will be conveyed to participants or nursing home leadership by direct conversation (in-person or via Zoom Conferencing) or by email.

G. Payment, including a prorated plan for payment: CNAs who participate in audio recordings will receive a \$50 incentive after completing the study (1 recording session before CHATO training and 3 recording sessions after CHATO).

H. Payment for a research-related injury: N/A – Participants will consent to being audio recorded while providing regular care to nursing home residents, no research-related injury is anticipated.

IV. Data Collection and Protection

A. Data Management and Security: The PI and research team will review all data to assure that any of the following demographic information has been removed (participant name, age, address, long term care facility name and location, dates, phone and fax numbers, social security numbers, medical record numbers, health plan beneficiary numbers, account numbers, and certificate or license numbers). It is not anticipated that the following identifiers will be present, but if present, these identifiers will also be removed (vehicle identifiers and serial numbers, device identifiers and serial numbers, web universal resource locators, internet protocol address numbers, and finger prints). A unique code number that has no connection to the identifying information will be assigned to each recording and demographic and survey data. The list that links the assigned code number to the subjects' identifying information will be kept by the PI and only disclosed as needed.

The research team will maintain one copy of the deidentified staff data archived in a computer solely dedicated to the study with information protections procedures in place specific to the data/communications internet computer environment. One backup copy of the data will be made in case of computer malfunction. This backup copy on CD, DVD, or external hard drive, will be kept in a double locked storage area. Other staff data will also be securely maintained in deidentified, secured files. Only selected research personnel will have access to this data. All research team members will be informed that study materials are not to be discussed or placed on the internet, so that incidental disclosure does not occur. Data will be maintained in a double locked file for seven years after this study is completed and then destroyed (at least 3 years after the final expenditure report submission). No identifiable data will be sent outside of KUMC.

1. **SPEEKO App:** The iPod Touch will run an iOS app that records and processes audio in real time and utilizes voice activation frequency technology to isolate and record when a user is speaking and discard periods of silence from the recording analysis. Original back-up recordings are saved locally on the secured iPod Touch for the Project Director to access through a master password within the app to all user accounts. All speech-related data are communicated using Transport Layer Security protocols to ensure end-to-end security and HIPAA compliance. The Project Director will download recordings for both groups and delete them from the iPod Touch.
2. **Audio Data:** All audio will be handled as confidential by assigning codes, not including names, from the point of archiving through data analyses. The original audio and file linking data identification codes to participants will be stored in locked secure files. Data access will be strictly controlled by the research protocol.

B. Sample / Specimen Collection: N/A

C. Tissue Banking Considerations: N/A

D. Procedures to protect subject confidentiality: The primary risk to participant confidentiality is accidental disclosure of audio recordings or other data outside the research team. Accordingly, all audio and other data will be handled as confidential by assigning codes, not including names, from the point of archiving through data analyses. The original audio and other data files and file linking data identification codes to participants will be stored in locked secure files. Data access will be strictly controlled by the research protocol. Any recordings or other data suggesting physical or mental harm or illegal behaviors will be reported to the NH administration and state authorities following mandated reporting guidelines. CNA staff risks of participation include anxiety at being recorded, but this is minimal. An additional risk is disclosure of recordings of their communication revealing performance, and survey responses to supervisory staff and administrators who may use this information for performance evaluations. Thus, NH administrators will not have access to recorded or other data that identifies individual staff or neighborhoods. Staff will be assured that recordings, descriptive data, and survey responses will not be shared with administrators, supervisory staff, or other staff. In addition, recordings that may be used for future training materials or presentations will not identify the CNA or their NH employer. No appreciable risk of physical, psychological, social, legal or other harm to staff participants is expected. No information about past, present, or future physical or mental health or payment of health care benefits (HIPAA protected information) will be collected. These procedures were utilized in the PI's R03 and R01 studies that analyzed video recordings from dementia care.

E. Quality Assurance / Monitoring

1. The PI and other research team members as delegated will conduct an audit at least annually including review of a random sample of at least 3 CNAs who participate in CHATO training and participate in audio recording for compliance with study protocols including informed consent documents, data storage documentation and deidentification of data. The PI will conduct an annual review of research team member compliance with IRB required training and certification. The PI or delegate will train and supervise research team members in recruitment and consenting procedures, data collection, provision of intervention, and data analysis and coding on a quarterly basis. Specific procedures to assure fidelity and compliance with the protocol are included in the research plan.
2. The **SMC** will initially review and approve the written study protocol, data collection and storage protocols, intervention materials, informed consent procedures, and this plan for data and safety monitoring. Any outside agreements with vendors and subcontractors will be reviewed. The SMC will also review the general reporting guidelines based on the study procedures approved by IRB. Reporting rules will be established taking into consideration the population under study and anticipated

adverse outcomes (reflected in the human subjects consent documents). Prior to study implementation, the SMC will identify pre-specified stopping rules that will be employed if significant benefits or risks have developed, if trial management issues prevent successful completion, or if compelling ethical concerns arise.

V. Data Analysis and Reporting

A. Statistical and Data Analysis:

1. **AIM 1.** Demonstrate feasibility, acceptability, and validity of the SPEEKO for Elderspeak feedback app use by staff in the NH. Five certified nursing assistants (CNAs) will use the app during NH care and provide feedback about any needed modifications. **Analysis:** A 10-item usability scale. Success will be determined by a cumulative score of 80% or more.
2. **AIM 2.** Test preliminary effects of an innovative self-monitoring feedback app on staff elderspeak use and compare accuracy to psycholinguistic analyses of audio-recorded staff communication. **Statistical Analysis:** Linear Mixed Models (LMMs) or Generalized LMMs, depending on the distribution of each outcome, will be developed to determine the impact of group assignment (feedback or no feedback) on use of elderspeak diminutives.
3. **AIM 3.** Evaluate app acceptability and costs. **Analysis:** Process-based costing to determine average costs for using the SPEEKO for Elderspeak feedback app, comparing costs relative to any difference determined for reductions in diminutive use in the immediate and delayed feedback groups.

B. Outcome:

1. **AIM 1 Expected Outcome:** The app will be readily used and acceptable to CNAs. Diminutive counts determined by the app will be correlated with psycholinguistic analysis, validating accuracy.
2. **AIM 2 Expected Outcome:** Staff who receive immediate app feedback (N= 30 in three NHs) will have greater elderspeak reduction after completing CHATO training compared to delayed feedback controls (N= 30 in three NHs).
3. **AIM 3 Expected Outcome:** Staff who use the app will find it acceptable and beneficial for their practice. Process-based costing will be used to determine costs for app use in NHs and other long-term service and support settings. Costs will be compared in relation to each group's outcomes.

C. Study results to participants: Audio recording feedback via the app will be provided either immediately after recording (treatment group) or at the end of the study (control group). Nursing homes will receive CHATO participation rate feedback.

D. Publication Plan: The PI will develop an appropriate plan for publication of research results based on the study aims and results.

VI. Bibliography / References / Literature Cited

1. Department of Health and Human Services. *National plan to address Alzheimer's disease: 2015 Update*. 2015.
2. Alzheimer's Association (2017). Alzheimer's Disease Facts and Figures.

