To facilitate dissemination, we developed interactive online CHAT modules (CHATo) that provide the same CHAT classroom content with the advantage of flexible and independent internet access for busy NH staff, including those in rural and small NHs.¹⁰ Recognizing the delay and incomplete adoption and application of evidence-based skills in practice, we believe additional strategies to optimize CHATo skills implementation are indicated.¹¹⁻¹³ Performance-based reinforcement of skills is effective in achieving greater immediate implementation and long-term maintenance of new skills use in practice.¹⁴ However, feasibility and costs for individualized expert feedback in NH settings are usually prohibitive and thus not widely used in practice.

This study will test feasibility and preliminary effects of an automated and performance-based feedback app that detects and reports the use of diminutives (terms of endearment such as honey, dearie, and sweetie) that are prevalent elderspeak terms linked to BPSD. The PI and colleagues developed the SPEEKO for Elderspeak app using our archived NH recordings to identify the most commonly used diminutives and then to develop algorithms

to detect them in speech.¹⁵ Building on proof of concept established in the laboratory, we propose to demonstrate feasibility of app use at the point-of-care and will then conduct a clinical trial to test preliminary efficacy of the app for amplifying reductions in diminutives use for NH staff completing the CHATO training.

SPECIFIC AIMS:

- 1) **AIM 1.** Demonstrate feasibility, acceptability, and validity of the SPEEKO for Elderspeak feedback app use by staff in the NH. Five certified nursing assistants (CNAs) will use the app during NH care and provide feedback about any needed modifications. **Hypothesis:** The app will be readily used and acceptable to CNAs. Diminutive counts determined by the app will be correlated with psycholinguistic analysis, validating accuracy.
- 2) **AIM 2.** Test preliminary effects of an innovative self-monitoring feedback app on staff elderspeak use and compare accuracy to psycholinguistic analyses of audio-recorded staff communication. **Hypothesis:** Staff who receive immediate app feedback (N= 30 in three NHs) will have greater elderspeak reduction after completing CHATO training compared to delayed feedback controls (N= 30 in three NHs).

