Audio recording supports precise measurement of verbal communication including duration, intensity, and patterns and is less invasive than videotaping, encouraging natural communication and maintaining privacy. Recordings can be reviewed repeatedly to verify accuracy and reliability. Limitations are (1) alteration of natural speech and behavior due to the awareness of recording and (2) inability to control for environmental factors such as noise. Research has established that NH staff do not significantly modify communication if recording is presented in a nonjudgmental manner^{60,61} and this was confirmed in the PI's

research.⁴³ The audio recording protocol is designed to measure communication in NHs⁶² and health care settings;⁶³ it was effective in the PIs research, uses measures to limit the Hawthorne effect (i.e., minimally obtrusive recording equipment), and will record each CNA during the same time periods from day to day to assure consistency.^{8,27,42-44,64,65}

Preliminary Effects Testing (Aims 2): We will test preliminary effects of app feedback on elderspeak use in audio-recorded staff communication. A cluster randomized trial will be conducted in six NHs that participate in CHATO training. We will compare the immediate and delayed-feedback control groups on elderspeak (diminutive) changes after participation in CHATO. We hypothesize that staff who receive immediate feedback will demonstrate greater reductions in use of diminutives, the most common and recognizable marker of elderspeak, compared to control group staff before they receive delayed feedback. We will validate app accuracy by comparing app results to psycholinguistic coding using our established protocols for data reduction, transcription, and coding.^{8,44,66}

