Six NHs will participate in audio recording of CNA communication before and after CHATO (see letters of support). These NHs will be randomly assigned to immediate feedback (n=3; recording with app feedback on elderspeak use) or control (n=3; recording with end of study feedback) groups. In each NH, 12 CNAs will be recruited using strategies successful in our past research such as announcing the research opportunity at staff meetings. Enrollment of 12 CNAs per NH allows for levels of attrition experienced in our prior studies. If fewer than 30 CNAs per group complete recordings, more NHs will be added. CNA volunteers (at least 30 per group) will record their communication in 2-hour care sessions on 1 day before and on 3 days after completing CHATO.

In both NH groups, 12 CNAs will be recorded for a 2-hour shift prior to participating in CHATO training (baseline). The URL link to complete the CHATO modules will be provided for the CNAs as well as other NH staff. Staff will be expected to complete the training over a 2-week period. After completion, the 12 CNAs from each NH who are participating in the app testing will be recorded again within a week of completing training (post-CHATO time 1), then approximately 1 week later (post-CHATO time 2), and finally another week later (post-CHATO time 3). Immediate feedback NH CNAs will receive the app feedback at the end of each post- CHATO recording session, while control group NH CNAs will not receive app feedback until the end of their post-CHATO time 3 recording sessions.

Each NH will provide a letter of interest, acknowledging random assignment, committing to engage staff in CHATO training, and agreeing to provide descriptive and cost data including number and types of staff and average wages. Each NH will be approved prior to participation by the KUMC IRB. NH size and census, profit status, proportion of residents with dementia, presence of a special care unit, staffing and turnover ratios, Medicare star rating, antipsychotic prescription rate, and Medicaid case mix will be collected from Nursing Home Compare and NH reports. Medicaid case mix is a measure of resident acuity or care needs that is used to determine Medicaid reimbursement rates and has been used in research to control differences in care needs across NHs.^{67,68} Participating NHs will be encouraged to engage all direct care staff, including housekeeping, dietary, and administrative staff in the training.

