Aim 1: We will demonstrate feasibility, acceptability, and validity of the SPEEKO for Elderspeak feedback app with detection model algorithm optimization with a diminutive accuracy testing benchmark of 80% or higher. App outputs will be compared to data from transcription and psycholinguistic coding, using our established protocols, to validate app reliability for diminutive detection. Also, an analysis of a CNA-completed, 10-item usability scale (The System Usability Scale) with an acceptability benchmark of 50% or higher.

Aim 2: Linear Mixed Models (LMMs) or Generalized LMMs, depending on the distribution of each outcome, will be developed to determine the impact of group assignment (feedback or no feedback) on use of elderspeak diminutives. Baseline diminutive use, group (feedback vs. no feedback), recording session (pre- and post CHAT sessions 1, 2, and 3), and interaction between intervention and session will be fitted as fixed effects. To account for clustering, each NH will be fitted as a random effect. To account for correlation due to repeated measurements, an appropriate covariance pattern will be determined from data. CNA and resident sex and CNA knowledge gain will be tested as covariates. Aim 2 will estimate variability, effect sizes, and intracluster correlation for a future larger-scale study. Sample sizes of as few as 30 in each group, or 10 CNAs on average in each NH, will achieve 80% power to detect a difference between the group means of 0.74 to 0.76 standard deviations, assuming the intracluster correlation coefficient ranging from 0.001 to 0.01 and coefficient of covariation among cluster sizes of 0.25. A two-tailed t-test was used with a significant level of 0.05 and the degrees of freedom based on the number of subjects.

Aim 3: We will use process-based costing to determine average costs for using the SPEEKO for Elderspeak feedback app, comparing costs relative to any difference determined for reductions in diminutive use in the immediate and delayed feedback groups.^{80,81}

D. Subject Criteria (See Vulnerable Populations appendix, if applicable):

1. Inclusion criteria: We will recruit CNAs who are age 18 or older, permanent employees, and fluent in English to participate. Descriptive information (age, sex, race, ethnicity, role, experience) will be used to identify CNA covariate factors predicting communication

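### The Aim 2 model uses baseline diminutive use both as a covariate and as an outcome, so post-session group differences look too precise; and no contrast is named as the test, although feedback starts only after the time 1 recording

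*Combined protocol and SAP*

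**What the plan says.** **Timing of feedback.** II.B (Preliminary Effects Testing) has one recording before CHATO and three after it, about a week apart. "Immediate feedback NH CNAs will receive the app feedback at the end of each post- CHATO recording session"; controls see theirs only once the time 3 recording is over. II.B (Audio Recordings) repeats this for both arms. No feedback is described at the pre-training recording.

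**Model.** In II.C the fixed effects are "Baseline diminutive use, group (feedback vs. no feedback), recording session (pre- and post CHAT sessions 1, 2, and 3"), plus the group-by-session interaction. Nursing home is a random effect, and the repeated-measures covariance pattern is to be chosen from the data.

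**Question asked.** I.A: "Staff who receive immediate app feedback (N= 30 in three NHs) will have greater elderspeak reduction after completing CHATO training". II.B: the trial will "compare the immediate and delayed-feedback control groups on elderspeak (diminutive) changes after participation in CHATO". II.C and V.A.2: the models are "to determine the impact of group assignment (feedback or no feedback) on use of elderspeak diminutives". None of these names a coefficient, session or contrast.

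**Power and purpose.** II.C claims "80% power to detect a difference between the group means of 0.74 to 0.76 standard deviations" with 30 CNAs per group, and adds: "A two-tailed t-test was used with a significant level of 0.05 and the degrees of freedom based on the number of subjects". It also says: "Aim 2 will estimate variability, effect sizes, and intracluster correlation for a future larger-scale study".

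**The concern.** There are two linked problems.

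1. *Baseline appears on both sides of the model.* The pre rows are predicted perfectly by the covariate, while the post rows are predicted only as well as the within-CNA correlation allows. A single slope fitted across all four rows is too steep for the post sessions, and the residual variance between CNAs is understated. A group difference read at the post sessions would then carry too small a standard error.

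2. *The test is not named, and the sessions are not alike.* Only times 2 and 3 follow feedback. The wording about change and the fitted interaction point to a 3-df test. The power statement points to a 1-df comparison of means with no session given. These estimate different things, and the analyst could choose between them after seeing the data.

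At stake are the error rate of any post-session mean comparison and the clarity of the effect size handed to the larger study.

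**Working it through.** **Step 1. The plan's power figure (II.C).** Inputs: 30 per group, two-sided 0.05, subject-based df = 30 + 30 − 2 = 58, cluster size 10, CV 0.25, ICC 0.001 to 0.01. Design effect = 1 + ((1 + 0.25²) × 10 − 1) × ICC = 1.0096 and 1.0962. Noncentral t gives a detectable difference of 0.739 SD at ICC 0.001. At ICC 0.01 it gives 0.770 SD, with power 0.789 at 0.76 SD (0.803 by the normal approximation). The plan's 0.74 to 0.76 SD is reproduced to within 2 power points. One unadjusted measure per CNA without clustering gives 0.736 SD, so the figure fits a 1-df t-test on group means, not a 3-df interaction.

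**Step 2. Effect of using baseline twice.** Assumptions not in the documents: linear mixed model, SD 1 at each session, equal correlation r (compound symmetry), complete data, no nursing home effect.

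- The covariate is constant within a CNA, so its slope comes from regressing the four-session mean on the pre value: b = (1 + 3r)/4. The right slope for a post session is r. At r = 0.5 that is 0.625 against 0.5.
- Actual variance per CNA of a mean over k post sessions, adjusted with b: (1 + (k − 1)r)/k − 2br + b².
- Variance the model believes: b(1 − b) − (1 − r)/4 + (1 − r)/k.
- SE ratio = √(model/actual). Large-sample null rejection = 2Φ(−1.96 × ratio).

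Worked case, r = 0.5, k = 3: actual = 0.6667 − 0.6250 + 0.3906 = 0.432; model = 0.2344 − 0.1250 + 0.1667 = 0.276; ratio = 0.80; rejection 11.7%.

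| r | b | Times 1–3: actual / model variance | SE too small by | Null rejection | Times 2–3: actual / model variance | SE too small by | Null rejection |
|---|---|---|---|---|---|---|---|
| 0.3 | 0.475 | 0.474 / 0.308 | 19% | 11% | 0.591 / 0.424 | 15% | 10% |
| 0.5 | 0.625 | 0.432 / 0.276 | 20% | 12% | 0.516 / 0.359 | 17% | 10% |
| 0.7 | 0.775 | 0.316 / 0.199 | 21% | 12% | 0.366 / 0.249 | 17% | 11% |

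Simulation with 30 per arm gave 15 to 22% and 10 to 13%. A repeat with 20,000 replicates, using 57 df, gave 9 to 12% rejection.

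**Step 3. What is not affected.** The covariate cancels from any contrast between sessions, so the interaction holds its 5% level (confirmed in both simulations).

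**Step 4. What the candidate tests estimate.** Let the effect be D at times 2 and 3 and zero before.

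- Mean of times 2 and 3: D.
- Mean of times 1 to 3: (0 + D + D)/3 = 0.67D. With half of D already present at time 1 through anticipation: (0.5D + D + D)/3 = 0.83D.
- Interaction: not diluted, but a 3-df test with no single estimate.

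**Step 5. Power with baseline used once.** Assumed D = 0.6 SD and r from 0.3 to 0.7. For a baseline-adjusted mean of k sessions the variance is (1 + (k − 1)r)/k − r², on 57 df. For the interaction λ = 15D²/(1 − r), on 3 and 174 df.

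| Test | r = 0.3 | r = 0.38 | r = 0.7 |
|---|---|---|---|
| Mean of times 1–3 | 63% | 63% | 78% |
| Interaction, 3 df | 63% | 68% | 95% |
| Mean of times 2–3 | 86% | 87% | 97% |
| Mean of times 2–3 on 4 df (six homes) | 65% | 66% | 82% |

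If a 0.6 SD effect appears only at time 3 (r = 0.38), the times 2 and 3 mean has 34% power and the interaction 55%.

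**The case against.** The strongest reply is that the model can already answer the question. With session categorical, time 1 has its own group coefficient and nothing is pooled. The hypotheses speak of reductions and changes, which with the fitted interaction point to differential change, and that test is neither diluted nor disturbed by the double use of baseline. All of this stands.

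A reader might infer that the plan dilutes its effect to two thirds and so misleads the next study: carrying 0.40 SD forward instead of 0.60 SD would take a simple 80%-power t-test plan from 45 to 100 per arm. The documents do not support that. Nowhere do they say that sessions will be averaged; the power statement names no session; and session-specific estimates would show time 1 beside times 2 and 3. An average over times 1 to 3 could also be defended as an effect of assignment that includes anticipation, given the assignment wording in II.C and V.A.2 and the intention-to-treat statement in II.B.

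A missing contrast in a trial labelled preliminary is, taken alone, close to missing detail. The double use of baseline is different, because it is a stated rule. It leaves the interaction intact, but not the post-session group means, and a comparison of group means is what the power statement describes. Leaving the covariance pattern open does not clearly rescue it: if pre is given its own variance, a slope of 1 fits the pre rows exactly and drives that variance to zero.

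It is also fair that the times 2 and 3 mean is not the best test in every case, as the last row of the power table and the time-3-only case show.

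**Conclusion.** The concern holds in this form. Using baseline as both covariate and outcome makes standard errors of group differences averaged over post sessions about 15 to 22% too small and raises null rejection to about 10 to 13%. This rests on a linear model with compound symmetry, correlations of 0.3 to 0.7, 30 per arm and no nursing home effect; a generalized model was not examined. The interaction is unaffected. In addition, time 1 precedes all feedback, and no term is named as the Aim 2 test. The 0.67D figure is conditional on a times 1 to 3 average that the plan does not state, and on no anticipation at time 1.

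A reader might also infer that the stated power is lost. It is not. With baseline used once, subject-based df, no nursing home effect and the plan's 0.74 to 0.76 SD present at times 2 and 3, the times 1 to 3 mean has 81 to 93% power and the interaction at least 82%.

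This should be fixed before data are analysed. The textual points are certain; the sizes depend on the assumptions above.

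**What to change.** In II.C and V.A.2:

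1. **Use baseline once.** Either (A) keep it as a covariate and model only the three post sessions as outcomes, or (B) keep pre as an outcome level and drop the covariate.
2. **Name one 1-df contrast before data are seen, with its df.** For example, under A, the group difference averaged over times 2 and 3. Under B, contrast times 2 and 3 with pre and time 1; this is a within-home comparison but assumes no anticipation at time 1 (with half of D there it estimates D − 0.25D = 0.75D).
3. **Report the time 1 group difference separately** as a check for imbalance or anticipation, and keep the interaction as a supporting test.
4. If the effect of assignment including anticipation is what is wanted, say so and name the times 1 to 3 average instead.

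The cost is wording in two sections, with no new data. The downsides of the times 2 and 3 average are that it uses two sessions instead of three and leaves out any anticipation at time 1. It also has less power than the interaction if the effect appears only at time 3, or if the mean is tested on 4 df and the correlation is about 0.38 or higher.
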